To produce a useful contrast with blueberries, a control food would ideally have several characteristics. These include: 1) low-to-no polyphenol content; 2) sugar content at least as high as blueberries (to enable ready caloric equilibration); 3) availability as a discrete item (to enable easier distribution and simplify instructions on consumption; 4) limited content of other biologically-active factors (e.g., fiber, minerals); 5) appeal to older adults; and 6) long shelf-life. Based on these criteria, we propose to study dates, which have considerable appeal to health-conscious elders, moderate fiber and potassium content (similar to blueberries), long shelf-life (in their dried form), and very low polyphenol content.(33) Conveniently, their high sugar density enables an isocaloric contrast with ~2 dates per day, maximizing ease and adherence among participants.

Significance

Each of our primary and secondary aims has important implications for the health of older adults, can be measured effectively with resources available through the Clinical Research Center (CRC), and has the potential to change in a 12-week period of observation. Moreover, our primary domains have already been linked directly or indirectly to polyphenol intake. This trial takes advantage of a unique partnership between a Harvard-affiliated teaching hospital, Beth Israel Deaconess Medical Center, a Harvard-affiliated geriatric research center, Hebrew SeniorLife, and a congregate living facility, NewBridge on the Charles, to determine a wide range of health effects of whole blueberry intake in older adults in an innovative, cost-efficient, and pragmatic manner.

4. Design

Principal research objective

To conduct a single-center, randomized, parallel-design experimental trial comparing whole frozen blueberries (equivalent to 1 cup of fresh blueberries) to an isocaloric control, with single-blind assessment of outcomes among approximately 46 women and 24 men. Participants must be aged 70 years or older and independent-living residents of NewBridge on the Charles for at least 3 months at randomization. For feasibility, the study uses a pragmatic intervention, comparing blueberries to 2 dried dates daily for 12 weeks. Our specific objectives are to determine the clinical and physiological effects of 12 weeks of daily blueberry consumption primarily on blood pressure, physical function, falls, and cognition in older adults.

5. Study Population and Eligibility

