The study population will consist of approximately 70 adults, aged 70 and older, who are independent-living residents of NewBridge on the Charles (NBoC) for at least 3 months at baseline. To enhance the generalizability of this trial, we have a few exclusion criteria. Eligibility will be determined over a series of contacts, including telephone contacts and in-person visits. Table 1 lists eligibility criteria.

Table 1. Eligibility Criteria.

Inclusion Criteria

• Age 70 and older• Independent-living• Resident of NewBridge on the Charles for at least 3 months• Willing to accept randomization to each fruit after tasting both options
Exclusion Criteria

• Myocardial infarction, stroke, or revascularization procedures ≤ 3 months prior to randomization• AHA Class III-IV heart failure• Active titration of blood pressure medication or titration within the last 3 months• Intolerance or allergy to blueberries or dates; allergy to tree nuts, peanuts, soy, or milk products• History of gastric bypass surgery• Planned hospitalization in the ensuing 4 months• Planned vacation lasting >1 week in the ensuing 4 months• Any current cancer treatment• End-stage renal disease• Any organ transplant• Uncontrolled diabetes mellitus with hemoglobin A1c $>9\%$• Inability to provide personal informed consent (e.g., cognitive impairment)• Seated systolic blood pressure > 200 mm Hg at Screening Visit• Investigator concern

6. Recruitment

Field Center

The trial will take place at a single center facility, NewBridge on the Charles, in Dedham, MA. NBoC is a senior living campus operated by Hebrew SeniorLife, a Harvard-affiliated, non-profit care organization. All recruitment and clinical visits, aside from phlebotomy, will be conducted in private space on the NBoC campus. Conducting the study visits at NBoC will be extremely convenient for participants and thus increase retention. Phlebotomy appointments will be conducted at the CRC in Boston, MA. Reimbursement for transportation (i.e. Lyft, Uber) or parking will be provided. All residents have freezers in their kitchens for blueberry storage. There will also be a freezer in the central kitchen dedicated to blueberry storage for later distribution.

Recruitment Strategies

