Screening Visit (SV): This in-person visit will be conducted at NBoC. It will include written informed consent, questions about demographics and confirming eligibility, a taste test of the frozen blueberries and dried dates, and a seated blood pressure measure to determine eligibility.

Wash-Out (WO): The Wash-Out will be the 1-2 week period leading up to the Baseline Visit. Participants will be asked to avoid all anthocyanin-rich foods for at minimum 1 week before baseline.

Baseline Visit (BV): After confirming eligibility and signed consent form and orally re-affirming consent, participants will complete fasting blood draw, spot urine collection, questionnaires, physical assessments, and set-up with a 24-hour ambulatory blood pressure monitor and Holter monitor. After successful completion of all BV data collection, participant will be randomized using REDCap. Participants will be given at least a 1-month supply of assigned fruit. They will also receive various handouts for compliance and adherence, tracking intake and falls, reporting unexpected events, and fruit pick-up.

Intervention (INT): Participants will receive a weekly email check-in from BV to FV to measure self-reported compliance with consuming study fruit and avoiding other anthocyanin-rich foods. The questionnaire will also include a section on reporting falls, as defined by the protocol. The purpose of the compliance questionnaire is to maintain rapport and improve adherence. If a participant does report a fall, study staff will call the participant within 3 days to administer the Fall Follow-Up Questionnaire. Additional fruit pick-ups will occur as needed.

Follow-Up Visit (FV): Participants will have an in-person visit at Week 12 after BV to re-do all BV assessments including phlebotomy, questionnaires, and physical function testing. Study staff will debrief with participants and provide some individualized results from the trial.

Table 2. Data collection schedule.

Study Visit Timeline	Visit 1 Screening (Week -2+)	Visit 2 Baseline (Week 0)	Week 4	Week 8	Visit 3 Week 12
Consent	X				
Demographic and medical questionnaires	X				
Vital signs	X				
Taste test	X				
24-hour electrocardiographic monitoring		X			X
24-hour ambulatory blood pressure monitoring		X			X
Fasting blood draw and spot urine		X			X
Randomization		X			
Fruit pick-up		X	X	X	
Compliance and STURDY questionnaires			X	X	X
Seated and standing blood pressure measures and anthropometrics		X			X
Physical function		X			X

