Taste test. Participants will be asked to taste a sample of each study fruit at the SV to ensure palatability. Responses will be recorded to document participant agreement to comply with either assignment at randomization.

Anthropometrics. Height will be measured at the BV using a floor stadiometer. Weight will be obtained at the BV and the FV using a digital calibrated scale.

Medications. Participants will provide a list of their current medications at the BV, which will be updated at the FV, if necessary.

Sleep. The Pittsburgh Sleep Quality Index will be administered at the BV and the FV. Participants can complete this questionnaire on their own, but it will be reviewed for

completeness and entered by study staff. The PSQI is a self-rated questionnaire which assesses sleep quality and disturbances over a 1-month time interval. Measures include subjective sleep quality, sleep latency, sleep duration, habitual sleep efficiency, sleep disturbances, use of sleeping medication, and daytime dysfunction. The sum of scores yields one global score. It has been shown to be consistent, valid, sensitive, and specific in distinguishing good and poor sleepers in research settings.

Incontinence. The Questionnaire for Urinary Incontinence Diagnosis will be given at the BV and the FV. QUID is a self-administered, 6-item questionnaire used to distinguish between stress urinary incontinence and urge urinary incontinence. It is a reliable and valid diagnosing tool for incontinence when compared to standard clinical evaluation in an outpatient setting.

Dietary Intake. The NHANES 2009-10 Dietary Screener Questionnaire (DSQ) will be given at the BV and the FV. It is a self-administered questionnaire, which asks about the frequency of consumption in the past month of selected foods and drinks. The DSQ captures intakes of fruits and vegetables, dairy/calcium, added sugars, whole grains/fiber, red meat, and processed meat.

Quality of Life. The CDC Health-Related Quality of Life Measures will be administered to participants at the BV and the FV. The HRQOL includes 4 self-reported questions related to overall health, physical health, mental health, and their effects on day-to-day living.

Cardiac ectopy. Atrial and ventricular premature beats will be detected by a 24-hour Holter monitor. Holter monitors will be fitted to participants at the BV and the FV and worn for at least 24-hours before returning them for data upload.

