- Performance monitoring with feedback – tracking enrollment and follow-up (observed/expected, overall and by key subgroups); monitoring missed visits, data completeness, protocol deviations, and data entry errors; distributing feedback through routine trial monitoring reports for the investigators, safety monitor, and IRB as needed. These reports, together with constructive feedback, have an important role in identifying and resolving issues expeditiously.

9. Randomization and Masking

Randomization

Random treatment assignment will be generated via a web-based system available to the research staff. Allocation uses centrally-allocated 1:1 permuted block randomization in blocks of 2 and 4. Eligibility and baseline data will be collected and entered into the database. The system will confirm eligibility and assign the study fruit.

Masking

Because this is a whole foods study, it is not feasible for treatment assignments to be masked to the participants or the research coordinator. Clinicians conducting ABPM and Holter readings and laboratory technicians will be blinded to study groups.

10. Intervention and Control Arms

This trial uses a pragmatic design to maximize generalizability and adherence. Participants randomized to the blueberry arm consume the equivalent of 1 cup of fresh blueberries daily in the form of frozen whole blueberries for 12 weeks. Blueberries are provided in a single-batch from the U.S. Highbush Blueberry Council. All participants have freezers in their apartments to store a supply of blueberries. Surplus storage will be kept in a freezer in the main kitchen for subsequent pick-ups at week 4 and week 8 after randomization.

Those in the control arm are asked to consume no blueberries and to consume an isocaloric portion of dried dates, equivalent to 2 dates daily for 12 weeks. All dates will be pitted and purchased from the same supplier. Dates are an ideal control because they have similar amounts of fiber, potassium, and calories compared to blueberries. The USDA estimates that dates contain approximately 1.6 mg of total polyphenols per 100 gm of edible content (~3 dates). By contrast, blueberries contain approximately 100 mg or more. Therefore, we expect a substantial anthocyanin difference between arms.

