Participants that share a residence will be randomized as a household. That is to say, the second participant from the same household enrolled in the study will not be randomized, but rather automatically assigned to the study fruit that their spouse was assigned. This approach is intended to prevent cross-contamination and promote adherence and statistical plans will account for clustering if multiple household members are enrolled.

In both arms, participants are asked to avoid other anthocyanin-rich foods, including blackberry, cherry, concord grape, cranberry, currant, eggplant, plum, purple potato, red and black raspberry, red cabbage, red wine, rhubarb, and strawberry.⁽⁴⁰⁾ Participants will be provided a list of foods to avoid. They will also receive counseling and materials at the BV and throughout the study on ways to track and incorporate the assigned fruit. All participants will also be asked to maintain their 'usual' lifestyle throughout the 12-week period. This includes restricting changes to their exercise, diet, medication use, and other behaviors.

11. Safety

Safety monitoring

The study will actively monitor participant safety. One aspect of safety monitoring is to evaluate screenees to determine whether it is safe for them to participate. Key safety related eligibility criteria are the exclusion of persons with (a) an intolerance or allergy to blueberries or dates or (b) allergy to tree nuts, peanuts, soy, or milk products. The dried dates procured for the study are purchased from a supplier that also handles tree nuts, peanuts, soy, and milk products.

A second aspect is monitoring enrolled participants for safety issues potentially related to the study. Surveillance for serious adverse events and other relevant clinical events will occur by questionnaire and contact with participants. If a participant develops a medical problem, the safety of continuing or resuming the study will be ascertained by the PI and other clinical study team members.

In addition, blood pressure values at the SV, BV, and FV will be compared to the alert values based on average seated measurement. All participants with an elevated seated blood pressure measurement (SBP >180 or DBP >110 mm Hg) should be asked if they have the following symptoms: headache, vision change, chest pain, shortness of breath, or change in urine color. Study physician and/or PCP will be notified as necessary.

Table 3. Blood pressure alert values.

Issue	Action

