Although the duration of the study is relatively short, the older study population increases the likelihood of medical events occurring unrelated to participation in this trial.

All serious adverse events and all unanticipated problems will be reported individually to [name] and the study PI within 7 days of when the research coordinator learned of the event.

In general, all other adverse events will be reported in aggregate form to the study PI and independent safety monitor at the time of regular data reports.

12. Analysis

Experimental design

We will conduct a single-center, randomized, parallel-design trial comparing whole frozen blueberries to an isocaloric serving of dried dates, with single-blind assessment of outcomes among 70 adults aged 70 years and older.

Analysis plan

The trial statistician will conduct all analysis of study data. Working with the PI, the statistician will develop an appropriate analysis plan. Our analyses will be conducted using the intention-to-treat principle, with linear regression models that adjust for baseline values as our primary statistical method.(41) If missing data exist (e.g., due to attrition), linear mixed models that incorporate both baseline and end-of-treatment values will be used. Because randomization in studies of this size can be imperfect, we will also adjust for any baseline characteristics that appear to be uneven (typically at $p < 0.10$). Because of the strong underlying hypotheses and correlated nature of our outcomes, we do not intent to adjust for multiple comparisons, but will treat results that are not corroborated by related outcomes with caution. Methods appropriate for clustered data (e.g., generalized estimating equations) will be used if multiple household members are recruited.

Power and sample size

We estimate power for our continuous endpoints, contrasting end-of-treatment values between arms (using $N=70$). With $\alpha=0.05$ and power=80%, we can detect a 0.68 standardized effect size. This is considered a medium-to-large-sized effect, similar to that tested in many studies of blueberries. With power=50% (i.e., aiming for an exact p -value=0.05), we can detect a 0.48 standardized effect size (medium). Thus, we should detect most moderate-to-large and many medium-sized effects. Thus, we should detect most moderate-to-large and many medium-sized effects.

13. Data Management

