Data will be collected from three main sources: 1) data collected by trial staff on case report forms for later entry into REDCap; 2) data entered by participants and/or trial staff directly into REDCap; and 3) data generated by ancillary facilities, such as laboratories, and sent to the trial analysis team directly. REDCap will only be accessible via the secure website and to authorized personnel. REDCap is a secure web application for building and managing online surveys and databases. It is secure behind the BIDMC firewall. All data collected on paper case report forms will be checked before data entry and maintained for later random audits. Any missing data will be marked as such, when possible. Data will be entered as soon as possible after it is collected.

Data confidentiality

All trial staff will be cognizant for strict controls to ensure data integrity. All staff with access to any portion of the study data will receive training on the importance of maintaining participant confidentiality, including appropriate BIDMC HIPAA training and CITI best research practices training. All data collected and stored electronically will be password protected and saved on secure servers. All study-related computers will be located behind BIDMC firewalls and maintain automated virus update mechanisms. Hard copies of data collection forms will be stored in secure areas (locked offices or cabinets). All staff will sign statements attesting to their understanding of and willingness to abide by policies designed to protect the integrity of the study data. General access to the data entry website is password protected with individual usernames and passwords. Data will be backed-up and checked periodically.

14. Timeline

The trial consists of three main phases: planning, implementation (recruitment, intervention, and data collection), and data analysis. Planning for the trial commenced in early 2020 but was put on hold due to COVID-19. Planning for the trial resumed in June 2021. Recruitment will be rolling, commencing in late 2021, and should last approximately 10 months, with randomization beginning within 1-2 months after recruitment. Participants will be followed for 12 weeks after randomization. Remaining time will be devoted to data analysis, presentation, and publication.

Table 5. General Timeline of the Effects of Blueberries in Older Adults Trial.

Activity	Month
Safety officer approval of final MOP	M3
Recruitment efforts and presentations begin	M3-5

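### Households are allocated through their first member, so a spouse who joins later enrols and gives baseline data knowing the fruit; the likely effect is small

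*Protocol*

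**What the plan says.** Protocol section 10 (Intervention and Control Arms) describes co-residents as randomised by household, and then defines how: "the second participant from the same household enrolled in the study will not be randomized, but rather automatically assigned to the study fruit" that the first member received. The reasons given are to avoid contamination within the home and to help adherence.

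For a participant who is randomised in the ordinary way, section 7 (Baseline Visit) fixes the order: "After successful completion of all BV data collection, participant will be randomized using REDCap". Section 9 gives the same order, with eligibility and baseline data entered before the system assigns the fruit.

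Three other statements bear on timing and knowledge:

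- Section 14 (Timeline): "Recruitment will be rolling, commencing in late 2021, and should last approximately 10 months".
- Section 9 (Masking): "it is not feasible for treatment assignments to be masked to the participants or the research coordinator". Readers of the ambulatory pressure and Holter recordings and laboratory technicians are blinded.
- Section 7: the research coordinator does most of the in-person data collection.

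Two provisions might be thought to help. Table 1 in section 5 requires each participant to be "Willing to accept randomization to each fruit after tasting both options", and the taste-test paragraph in section 7 adds "Responses will be recorded to document participant agreement to comply with either assignment at randomization". Section 12 says "Methods appropriate for clustered data (e.g., generalized estimating equations) will be used if multiple household members are recruited".

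**The concern.** A household can be randomised as a unit without losing concealment, provided that everyone who will join is committed and measured before the allocation is known. The Protocol does not require this. A second spouse who comes forward after the first has been allocated already has the study fruit at home. That spouse chooses whether to join knowing what the assignment will be, and the coordinator who screens and assesses the spouse knows it too.

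Spouses who join knowing the fruit is blueberries may differ from those who join knowing it is dates. Any such difference comes from self-selection and not from randomisation, so the primary test does not allow for it. Baseline adjustment would remove only part of it. An analysis plan cannot restore concealment once it is lost; the order of enrolment and allocation is a protocol procedure.

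**Working it through.** **Does the sequence allow foreknowledge?** Section 7 places allocation after baseline for the person being randomised. Section 10 exempts the second household member from randomisation and says nothing about when that member's consent or baseline must take place. Rolling entry over about 10 months allows spouses to enter at different times, and participants and coordinator are unmasked. Foreknowledge is therefore possible, and no section rules it out.

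**Do the existing provisions close the gap?** Willingness to eat either fruit narrows selection by taste, but a spouse who already knows the fruit faces no random assignment. Generalised estimating equations and similar methods deal with correlation between spouses, not with who chose to join.

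**Scale.** The Protocol has no figure for this point; its power statement (section 12) gives the scale. With 35 per arm and two-sided alpha 0.05 (sidedness assumed), the noncentral t gives a detectable effect of 0.679 SD at 80% power and 0.475 SD at 50%. The stated 0.68 and 0.48 reproduce.

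**Inputs for the illustration.** From the Protocol: N = 70, 1:1 allocation, baseline-adjusted linear regression. Assumed, because the Protocol does not give them:

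- number of late joiners: 7, 14 or 21 (share s = 10%, 20% or 30%);
- difference δ between late joiners in the two arms: 0.25 or 0.5 SD, equal at baseline and follow-up;
- baseline to follow-up correlation r: 0.5 or 0.7.

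**Formulas.** Bias after baseline adjustment = s × δ × (1 − r). SE = √(2/35 × (1 − r²)), which is 0.207 SD at r = 0.5 and 0.171 SD at r = 0.7. Type I error = P(|Z| > 1.96) when Z is shifted by bias/SE. For example, 14 joiners, δ = 0.5 and r = 0.5 give 0.20 × 0.5 × 0.5 = 0.050 SD, a shift of 0.050/0.207 = 0.24, and an error of 5.67%.

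| r | Late joiners | δ (SD) | Bias (SD) | Type I error |
|---|---|---|---|---|
| 0.5 | 7 | 0.25 / 0.5 | 0.0125 / 0.025 | 5.04% / 5.17% |
| 0.5 | 14 | 0.25 / 0.5 | 0.025 / 0.050 | 5.17% / 5.67% |
| 0.5 | 21 | 0.25 / 0.5 | 0.0375 / 0.075 | 5.38% / 6.52% |
| 0.7 | 7 | 0.25 / 0.5 | 0.0075 / 0.015 | 5.02% / 5.09% |
| 0.7 | 14 | 0.25 / 0.5 | 0.015 / 0.030 | 5.09% / 5.35% |

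**Simulation check.** 20,000 baseline-adjusted regressions per case (n = 70, no within-household correlation, Monte Carlo SE about 0.15 percentage points) gave, at r = 0.5: 5.2% with no late joiners; 5.2% and 5.0% with 7; 5.1% and 5.7% with 14 (mean bias 0.027 and 0.048 SD). At r = 0.7 with 14 joiners and δ = 0.5, mean bias was 0.030 SD and the error 5.3%.

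**How many late joiners are possible?** Section 4 plans "single-blind assessment of outcomes among approximately 46 women and 24 men". If couples are mixed-sex (an assumption), 7, 14 and 21 late joiners need 7/24 = 29%, 14/24 = 58% and 21/24 = 88% of the men to be in such couples. With the roughly 40% male given in section 2 (28 men), the shares are 25%, 50% and 75%. So 21 is near the maximum.

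**Stress test.** Suppose baseline adjustment removes none of the difference and SE = √(2/35) = 0.239 SD. With 10 late-joining second members and a residual difference of 0.5 SD, bias is 0.071 SD and the error 6.0%; with 15, 0.107 SD and 7.3%. In the extreme corner of 24, with every planned man in a couple whose second member joins late, they are 0.171 SD and 11.1%.

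**The case against.** The best reply is that the harm depends on an event the Protocol does not describe. It fixes how a second member is assigned, not that spouses enter at different times. A couple screened together and entered one after the other fits the text, and visit scheduling may be settled in the manual of procedures, which is not at hand. That limits how often the problem could arise, and late joiners may indeed be zero. Spouses who both finish baseline before allocation are unaffected. But the rule, followed as written, permits the loss of concealment.

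It is also fair that the 0.25 to 0.5 SD difference has no source, that tasting and accepting both fruits narrows selection by preference, and that most of the simulated cases cannot be told apart from no effect. The largest bias for 7 to 14 joiners, 0.050 SD, is about 7% of the 0.68 SD detectable effect (0.050/0.68). These points stand and keep the matter minor.

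The primary outcome, average wake-time ambulatory systolic pressure, is recorded by a device and read blind, so the issue there is who joins and not how they are measured. Baseline measures taken by the coordinator (physical performance, grip strength) or self-reported (sleep, incontinence) are more exposed, though no size is put on that here.

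Finally, the household rule is a reasoned choice with a stated purpose. That purpose is kept in full if the household is still given one fruit but is allocated only once all its joining members are in.

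**Conclusion.** The concern holds, as a minor weakness. Under the rule as written, allocation is concealed for the first household member but not for a spouse who joins after that member's allocation, and nothing else in the Protocol restores concealment. With 7 to 14 late joiners and the assumed differences, bias in the primary contrast is 0.008 to 0.050 SD and type I error 5.0 to 5.7% across correlations of 0.5 to 0.7. With 21, near the maximum, type I error is 5.4 to 6.5% at a correlation of 0.5. The number of late joiners, the size of their difference and the correlation are all assumptions. The conclusion about concealment does not depend on them; the judgement that the effect is small does.

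**What to change.** In section 10, state that a household is randomised once, and only after every member who intends to join has given consent, tasted both fruits, been found eligible and completed all baseline data. Add a pre-screening question on whether a co-resident will take part. Flag in the database anyone who still enrols after the household's allocation, keep that person in the intention-to-treat analysis, and report a sensitivity analysis of the primary outcome without such participants. The primary estimate would still carry whatever bias those remaining few bring; the sensitivity analysis shows whether it matters.

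The change needs one or two sentences, one question and one database field. The practical cost is coordinating spouses' baseline visits, each with its own wash-out, fasting blood draw in Boston and 24-hour monitoring, which may delay some first members. Residence on the study campus should make this easier.
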